4.13 Deviations from SAP

Any deviations from the statistical analysis plan will be described and justified in the final clinical trial report.

4.14 Changes in Conduct or Planned Analyses from the Protocol

There have been no changes in planned analyses from those defined in the protocol.

If any analysis, definitions, or summaries that have been written in the protocol have been amended for the purpose of the analysis, these will be described and justified in the final clinical trial report. This may include:

- Changes to populations
- Additional analysis
- Changes to equations
- Additional data to analyze

4.15 Algorithms/SAS Codes

- **Tables that need descriptive statistics – continuous variables:**

```
PROC UNIVARIATE DATA=dset NOPRINT;
  VAR var1 var2 var3 ... varn;
  BY byvar; (optional)
  OUTPUT OUT=outname
  N=n MEAN=mean MIN=min MAX=max MEDIAN=median STD=std;
  RUN;
```

- **Tables that need frequency counts:**

```
PROC FREQ DATA=dset NOPRINT;
  BY byvar; (optional)
  TABLES var1*var2;
  OUTPUT OUT=outname;
  RUN;
```

- **Tables that need exact or asymptotic 95% CIs between groups for proportions:**

```
PROC FREQ DATA=dset;
```

CONFIDENTIAL

Sponsor:	Zealand Pharma A/S	Protocol Number:	ZP4207-16137
----------	--------------------	------------------	--------------

BY byvar; (optional)
*TABLES var1 * var2 / MEASURES RISKDIFF ALPHA=0.05;*
EXACT MEASURES;

RUN;

Notes: 1 Estimates are computed for 2x2 tables only

2 This code also gives exact 95% CIs within group for binomial proportions

- **Tables that need 95% CIs within group for binomial proportions:**

PROC FREQ DATA=dset;
BY byvar; (optional)
TABLES var1;
EXACT BINOMIAL;
RUN;

- **Tables that need 95% CIs within group for continuous variables:**

DATA outdata;
SET outname;
LCL=mean-(TINV(0.975,n-1)(std/SQRT(n)));*
UCL=mean+(TINV(0.975,n-1)(std/SQRT(n)));*
RUN;

- **Tables that require generalised linear modelling, including 95% CIs:**

PROC GENMOD DATA= dset;
CLASS class variables;
MODEL 'Responses / Attempts' = <effect> <treatment> /DIST=BIN;
LSMEANS treatment / DIFF CL;
ESTIMATE Drug 1 vs. Placebo' treatment 1 0 0 -1 /EXP;
ESTIMATE Drug 2 vs. Placebo' treatment 0 1 0 -1 /EXP;
ESTIMATE 'Drug 3 vs. Placebo' treatment 0 0 1 -1 /EXP;
BY byvar; (optional)
WHERE wherever; (optional)
RUN;

Note: (Treatment order: 1=drug 1,2= drug 2,3= drug 3, etc... 5= placebo)

- **Tables that require analysis of (co)variance and 95/90% CIs between arms for continuous variables:**

PROC GLM DATA= dset OUTSTAT=outset;
CLASS class variables;
MODEL response = <effect> <treatment> / SOLUTION;
*LSMEANS treatment / STDEERR PDIFF CL; *ADD: ALPHA=0.1 for 90% CIs;*
*ESTIMATE 'T1 - T2' treatment 1 -1 0; *or 'T2 - T1' treatment -1 1 0 if applic.;*
ESTIMATE 'T1 - T3' treatment 1 0 -1;
ESTIMATE 'T2 - T3' treatment 0 1 -1;
BY byvar; (optional)

CONFIDENTIAL

Sponsor:	Zealand Pharma A/S	Protocol Number:	ZP4207-16137
----------	--------------------	------------------	--------------

WHERE wherever; (optional)

RUN;

QUIT;

Note: (Treatment order: 1=drug 1,2= drug 2,3= drug 3, etc... 5= placebo)

- **Tables that present Fisher's Exact or CMH:**

PROC FREQ DATA=dset NOPRINT;

BY byvar; (optional)

*TABLES var1*var2/CMH score=MODRIDIT EXACT;*

OUTPUT OUT=outname CMH EXACT;

RUN;

- **Tables that need to use WILCOXON:**

PROC NPAR1WAY DATA=dset WILCOXON;

CLASS class variables;

VAR variable;

RUN;

- **Tables that need a regression slope and 90 % CI:**

PROC MIXED DATA=dset NOCLPRINT NOITPRINT;

MODEL lnauc=lntrt /S CL ALPHA=.1;

MAKE 'SOLUTIONF' OUT=outstats NOPRINT;

RUN;

- **Tables that need number of events/censored and probabilities of failure/survival at cut off times:**

PROC LIFETEST DATA=dset OUTSURV=LIFE METHOD=KM INTERVALS=12, 24,;

*TIME duration*censor (0 or 1);*

ID subject;

STRATA treatment;

RUN;

- **Tables that need life table with estimates of survival, with CIs and log rank test:**

PROC LIFETEST DATA=dset OUTSURV=LIFE METHOD=KM;

*TIME duration*censor (0 or 1);*

ID subject;

STRATA treatment;

RUN;

- **The calculation of AUC using trapezoidal method (Area of segment (ab) = (b-a)*(f(a) + f(b))/2:**

DATA auc (KEEP = pid area);

RETAIN A FA AREA 0;

SET dset;

BY pid time;

CONFIDENTIAL

Sponsor:	Zealand Pharma A/S	Protocol Number:	ZP4207-16137
----------	--------------------	------------------	--------------

```

IF FIRST.pid THEN DO;
  A = TIME;
  FA = <FEVI>;
  AREA = 0;
END;
ELSE DO;
  AREA = AREA + (TIME -A)*((FA+<FEVI>)/2);
  A = TIME;
  FA = VALUE;
END;
IF LAST.pid THEN OUTPUT;
RUN;

```

5 Tables and Listings

5.1 Table Format

All output will be produced using SAS version 9.4 or a later version.

In the top left portion of each table/listing, a *table/listing number* followed by the *title* of the table/listing will be presented. After the title line, optional *sub-title* or *population* information can be presented. Horizontal lines will appear before and after the column heading of the table/listing. *Footnotes* will be put under the main body of text at the bottom of the page.

The *sponsor name*, *protocol number*, programmers User ID, status of the table/listing (i.e. draft or final) and *SAS program name* will appear bottom left in a string and the *page number* will appear on the bottom right corner of each table/listing. The *date and time of creation* of table/listing will appear bottom left under the sponsor name. The source listing number will appear bottom left.

A *landscape layout* is proposed for both table and listing presentations.

The *left and right margins* of all tables and listings will be a minimum of 2.1 cm from the left and 1.9cm from the right. The *top and bottom margins* will be a minimum 2.92cm. *Header and footer* will be both 1.27 cm.

There is no special requirement of *font type and size*, but an *8-point* font size for tables and *7-point* for listings is proposed using *Courier New* font. A maximum SAS line size=141 and page size=44 for *8-point* font size, and line size=161 and page size=50 for *7-point* will be used so as to fit on both UK and US paper sizes.

In a listing, in the case that a subject's record has been continued to the next page, an appropriate identification (e.g., the subject ID number) must be presented at the beginning of that page.

CONFIDENTIAL

Sponsor:	Zealand Pharma A/S	Protocol Number:	ZP4207-16137
----------	--------------------	------------------	--------------

5.2 Conventions

Unless otherwise specified, in summary tables of continuous variables, the minimum and maximum values will be displayed to the same number of decimal places as the raw data, the mean and median will be presented to one extra decimal place compared to the raw data, and the standard deviation will be displayed to two extra decimal places compared to the raw data. PK and PD data will be reported with 3 significant digits. Wherever possible data will be decimal aligned.

Unless otherwise specified frequency tabulations will be presented by number and percentage, where the percentage is presented in brackets to 1 decimal place.

P-values, if applicable, will be presented to 3 decimal places. If a p-value is less than 0.05 but is greater than or equal to 0.01, then an asterisk (*) will be added next to this value. If a p-value is less than 0.01 but is greater than or equal to 0.001, then two asterisks (**) will be added next to this value. Finally, if the p-value is less than 0.001 then three asterisks (***) will be added next to this value and it will be presented as <0.001. If the rounded result is a value of 1.000, it will be displayed as >0.999. Any date information in the listing will use the *date9.* format, for example, 06OCT2017. In the listing, a unit associated with a variable will be presented only once within parentheses either below or next to that variable in the heading portion. If a parameter has multiple units, each unit will be displayed only once, as applicable.

All tables will have their source listing referenced in a footnote. Listings should be sorted by treatment group, subject and visit and have the source data received by data management referenced in a footnote. All tables and listings will be converted into Microsoft Word documents and collated into two complete documents.

The following conventions apply for calculation of PK parameters:

- Any BLQ (<LLOQ) values that occur before the first quantifiable concentration will be replaced with zero.
- If a BLQ (<LLOQ) value occurs after a quantifiable concentration in a profile and is followed by a value of LLOQ or above, then the BLQ (<LLOQ) will be replaced with LLOQ/2.
- If two BLQ (<LLOQ) values occur in succession, the profile will be deemed to have terminated at the final quantifiable concentration and subsequent LLOQ or above values will be treated as 'missing'.

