4.5 Exposure

The exposure to trial medication (dasiglucagon or GlucaGen) for evaluation of pharmacokinetics will be assessed based on plasma concentration data from samples collected at the dosing visit (Visit 2):

CONFIDENTIAL

Sponsor:	Zealand Pharma A/S	Protocol Number:	ZP4207-16137
----------	--------------------	------------------	--------------

- Area under the drug concentration curve from time zero to 90 minutes, $AUC_{0-90\text{ min}}$.
- Maximum plasma drug concentration (C_{\max}).
- Time to maximum plasma drug concentration (t_{\max}).

Samples (including back-up samples) will be collected pre-dose, and at 15, 30, 35, 40, 50, 60, 90, and 120 minutes after dosing. The actual time of blood sampling for exposure to trial medication should not deviate from the nominal time by more than ± 1 minute. Pre-dose is defined as within 2 minutes prior to dosing.

All data collected related to study drug administration will be provided in the data listings.

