4.7.5.1 Analysis of exposure (PK) endpoints

AUC will be derived as the area under the individual plasma dasiglucagon/GlucaGen concentration profile for PK from 0 to 90 minutes or last valid measurement if this measurement is assessed sufficiently close to 90 minutes (decision to be taken at the blinded data review meeting). The standard trapezoidal method will be used, based on actual rather than nominal timepoints.

Cmax will be determined as the maximum of all valid plasma dasiglucagon/GlucaGen concentrations.

Tmax will be determined as the timepoint where the maximum of all valid plasma dasiglucagon/GlucaGen concentration measurements for each measurement series is observed.

The log-transformed PK endpoints AUC and Cmax will be analyzed in the same way as the AUC endpoints.

As tmax is a highly discrete endpoint, Wilcoxon's rank sum test for unpaired observations will be used to assess differences between the two treatment groups.

Exposure endpoints will be summarised for the Full analysis set, which is identical to the Safety analysis set.

CONFIDENTIAL

Sponsor:	Zealand Pharma A/S	Protocol Number:	ZP4207-16137
----------	--------------------	------------------	--------------

Table 4-2: Overview of Efficacy Analyses

Efficacy Endpoint	Statistical Analyses	SAS Procedure
Endpoints with binary response outcomes:		

 Plasma glucose recovery within 30 minutes, within 20 minutes, within 15 minutes, and within 10 minutes after study drug injection without administration of rescue IV glucose. 	
 Fisher's exact test for each pairwise comparison 	
 FREQ LOGISTIC
Endpoints with continuous outcomes:		

 Plasma glucose changes from baseline changes from baseline within 30 minutes, within 20 minutes, within 15 minutes, and within 10 minutes after study drug injection or at the time of rescue. 	
 Changes from baseline: Analysis of Covariance model, with treatment group modeled as a fixed effect and with the baseline plasma glucose modeled as a covariate Changes from baseline: Two sided t-test at the 0.05 significance level 	
 GLM
Endpoints with time-to-event outcomes:		

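### The two-BLQ rule cuts a profile that is below LLOQ at 90 and 120 minutes back to 60 minutes or earlier, so AUC0-90 is either not derived or is a shorter area under the same label

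*SAP*

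**What the plan says.** SAP section 4.5 defines the exposure endpoint as "Area under the drug concentration curve from time zero to 90 minutes" and gives the sampling scheme: "Samples (including back-up samples) will be collected pre-dose, and at 15, 30, 35, 40, 50, 60, 90, and 120 minutes after dosing".

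Section 4.7.5.1 derives the area to 90 minutes, or to the "last valid measurement if this measurement is assessed sufficiently close to 90 minutes", and leaves that call to the blinded data review meeting. No numeric limit is attached. On method it says: "The standard trapezoidal method will be used, based on actual rather than nominal timepoints". Log AUC goes into an ANCOVA and is reported as a ratio of geometric means, as for the glucose AUC in section 4.7.4.1.

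Section 5.2 has three rules for BLQ values:

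- Values before the first quantifiable concentration become zero.
- A BLQ value after a quantifiable one, if it is "followed by a value of LLOQ or above, then the BLQ (<LLOQ) will be replaced with LLOQ/2".
- For a run of BLQ values: "If two BLQ (<LLOQ) values occur in succession, the profile will be deemed to have terminated at the final quantifiable concentration". Any quantifiable result after that point is discarded.

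No rule gives a number to a BLQ sample that trails the last quantifiable one.

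**The concern.** A profile that has fallen below LLOQ by 90 minutes is an ordinary, foreseeable pattern, and the concentration at 90 is then known to lie between zero and LLOQ. The area to 90 minutes is therefore almost fully determined. The two-BLQ rule discards that knowledge and ends the profile at least 30 minutes short of the endpoint's own window.

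What follows is left to the review meeting. Leaving the value out and accepting a shorter area move the mean in opposite directions. The rules also treat near-identical data differently: whether a subject keeps the last third of the window depends on the 120-minute sample, which lies outside the window.

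The comparison at stake is dasiglucagon against GlucaGen. Section 3.8 has samples matched to the applicable bioanalytical assay, so the LLOQ may differ between the two drugs. If so, the ratio of geometric means could shift for assay reasons rather than because of the drugs.

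**Working it through.** The SAP states no LLOQ, BLQ share or expected AUC, so there is no figure of its own to reproduce.

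**1. Where the profile ends.** With BLQ at 90 and 120, the last quantifiable sample is at 60 minutes at the latest. Coverage is at most 60/90 = 67% of the window, and the gap is at least 90 - 60 = 30 minutes.

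**2. Two subjects with the same samples up to 90.** Both have C60 at or above LLOQ and are BLQ at 90.

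- Subject A is quantifiable at 120. The 90-minute value becomes LLOQ/2, and the last trapezoid is 30 × (C60 + LLOQ/2)/2 = 15·C60 + 7.5·LLOQ.
- Subject B is BLQ at 120. The profile is cut at 60, so the last trapezoid is lost or the AUC is not derived.

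If B is truncated, A's area exceeds B's by 15·C60 + 7.5·LLOQ. As C60 is at least LLOQ, that is at least 22.5·LLOQ (concentration × minutes).

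**3. How uncertain is B's area?** With C90 between 0 and LLOQ, the last trapezoid lies between 15·C60 and 15·C60 + 15·LLOQ. Setting C90 to LLOQ/2 takes the midpoint, so the error is at most 7.5·LLOQ. Truncation loses at least 15·C60, hence at least 15·LLOQ: never less than twice the largest imputation error.

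**4. Effect on the geometric mean.** Let p be the share affected.

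- If dropped: log shift = p × (mean log AUC of retained - mean log AUC of affected).
- If truncated: log shift = p × mean log(truncated area / full area) among the affected.

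These were evaluated on simulated one-compartment profiles at the SAP sampling times. All inputs are assumptions: half-life 15 to 30 minutes; between-subject log-SD 0.4 for scale, 0.25 for elimination and 0.3 for absorption; LLOQ set at the quantile of the 90-minute concentration that gives each p.

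| Share BLQ at 90 and 120 | Dropped | Truncated at 60 |
|---|---|---|
| 5% | +4% | -0.3% to -0.9% |
| 10% | +7% | -1% to -2% |
| 20% | +14% | -2% to -4% |
| 40% | +27% to +28% | -5% to -9% |

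With slower absorption, and with the cut made at the last quantifiable sample (sometimes before 60), the 40% truncation figure reaches about -12%.

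A second set of assumptions used an absorption half-time of 10 minutes, a half-life of 15 or 30 minutes and a CV of the scale factor of 30% or 60%. With 30% affected it gave +17% to +30% if dropped and -3% to -7% if truncated. Hand check of one case (half-life 30 minutes, CV 30%): the 60-90 minute segment is 19.3% of the area in affected subjects, and exp(0.3 × ln(1 - 0.193)) = 0.938, as simulated.

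**5. Effect of the remedy.** LLOQ/2 at 90 minutes gave a geometric mean within 1% of the full-profile value in every scenario. That covers profiles still quantifiable at 60. Where 60 is already BLQ, the remedy puts LLOQ/2 at 60 and zero at 90. With that applied in full, the error stayed within 1% up to 20% affected and reached about 3% low at 40% affected in the slowest profiles.

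**The case against.** The strongest counter-argument is that nothing in the SAP removes anyone. Section 5.2 sets only later values at or above LLOQ to missing, not the AUC or the subject. Section 4.7.5.1 provides for a profile that stops early and summarises exposure on the Full analysis set. The valid-cases wording in section 4.12 follows a sentence about subject withdrawal, not BLQ results. A reader might infer that these subjects have no AUC0-90, that the lowest-exposed are left out, and that mean exposure is therefore biased upward. The documents do not support that reading. The choice is left to the blinded review, and the bias can go either way. BLQ at 90 also reflects fast elimination: in the second set of scenarios only 46% to 87% of affected subjects were truly among the lowest by AUC.

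It can also be said that section 4.7.5.1 asks for a valid measurement, not a quantifiable one, so a BLQ result at 90 might itself count. That is possible, but section 5.2 declares the profile ended before it and gives no value to use.

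Finally, the sizes rest wholly on assumptions, and the number affected may be zero. That stands. What survives is that a written rule cuts off area that the data nearly determine, and treats subjects A and B differently because of a sample outside the window.

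**Conclusion.** The point holds as a minor defect in the derivation rules, with the direction of bias left open. For a subject BLQ at 90 and 120 minutes, sections 5.2 and 4.7.5.1 together lead to no AUC0-90 or to an area ending at 60 minutes or earlier under the AUC0-90 label. On the assumed profiles with 5% to 40% affected, the geometric mean moves by about +4% to +28% in the first case and about 0% to -12% in the second. There is no effect if nobody is BLQ at both times, and without an LLOQ the documents cannot show how many would be. The endpoint is an other-secondary PK endpoint (section 2.2) and is not in the testing order of section 4.7.1, so the confirmatory conclusions do not depend on it.

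**What to change.** Change sections 5.2 and 4.7.5.1 before the treatment codes are released:

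- For AUC0-90, BLQ samples up to 90 minutes that follow the last quantifiable concentration count as valid. The first is set to LLOQ/2 and any later ones to zero, and the area is computed to 90 minutes for every such subject.
- The review meeting's judgement on whether the last sample is near enough to 90 minutes applies only when samples are missing, not when they are BLQ.

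The cost is about two sentences. The downside is that imputed values below LLOQ enter the area. By step 3 the error is at most 7.5·LLOQ for a profile still quantifiable at 60 minutes, and LLOQ/2 at 90 changed the geometric mean by less than 1% in the assumed scenarios. LLOQ/2 followed by zero is one convention among several; what matters is that one is fixed in advance and gives every such subject an area over the same window.

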5.3 Tables

5.3.1 Section 14.1: Baseline and Demographic Data

- Table 14.1.1 Patient Disposition
- Table 14.1.2 Discontinuation and Drop-outs
- Table 14.1.3 Demographic and Baseline Characteristics
- Table 14.1.4 Medical History/Concomitant Illness
- Table 14.1.5 Summary of Diabetes Duration

CONFIDENTIAL

Sponsor:	Zealand Pharma A/S	Protocol Number:	ZP4207-16137
----------	--------------------	------------------	--------------

Table 14.1.6 Concomitant Medication
 Table 14.1.7 History of Alcohol/Drug Abuse

5.3.2 Section 14.2: Efficacy Analysis Data

Table 14.2.1 Summary of Plasma Glucose Concentrations
 Table 14.2.2 Summary of Plasma Dasiglucagon Concentrations
 Table 14.2.3 Summary of Plasma GlucaGen Concentrations

5.3.3 Section 14.2: Primary Confirmatory Endpoint

Table 14.2.4 Time to Plasma Glucose Recovery
 Table 14.2.5 Time to Plasma Glucose Recovery without Censoring Rescue IV Glucose Subjects
 Table 14.2.6 Time to Plasma Glucose Recovery with Censoring at the Time of Rescue IV Glucose Administration

5.3.4 Section 14.2: Secondary Endpoints

Table 14.2.7 Plasma Glucose Recovery within Defined Time Points
 Table 14.2.8 Plasma Glucose Changes from Baseline within Defined Time Points
 Table 14.2.9 Time to First Plasma Glucose Concentration of ≥ 70 mg/dL

5.3.5 Section 14.2: Exposure (PD/PK) Endpoints

Table 14.2.10 Summary Statistics of Pharmacodynamics Endpoints
 Table 14.2.11 Statistical Analysis of Pharmacodynamics Parameters
 Table 14.2.12 Summary Statistics of Pharmacokinetic Endpoints
 Table 14.2.13 Statistical Analysis of Pharmacokinetic Parameters

5.3.6 Section 14.2: Exploratory

Table 14.2.14 Time to First Plasma Glucose Concentration of ≥ 70 mg/dL or Increase of ≥ 20 mg/dL within 30 Minutes
 Table 14.2.15 Summary Statistics of Plasma Insulin Response

5.3.7 Section 14.3: Safety Analysis Data

5.3.7.1 Adverse events

Table 14.3.1.1 Overview of Incidence of TEAEs
 Table 14.3.1.2 Summary of TEAEs by MedDRA System Organ Class and Preferred Term
 Table 14.3.1.3 Summary of TEAEs by Severity, Relationship, Seriousness, and Outcome
 Table 14.3.1.4 Summary of TE AESIs by Severity, Relationship, Seriousness and Outcome

5.3.7.2 Laboratory results

Table 14.3.2.1 Summary of Hematology Data – Actual and Change from Pre-Dose Measurement
 Table 14.3.2.2 Summary of Biochemistry Data – Actual and Change from Pre-Dose Measurement

CONFIDENTIAL

Sponsor:	Zealand Pharma A/S	Protocol Number:	ZP4207-16137
----------	--------------------	------------------	--------------

- Table 14.3.2.3 Summary of Coagulation Data – Actual and Change from Pre-Dose Measurement
- Table 14.3.2.4 Summary of Urinalysis Data – Actual and Change from Pre-Dose Measurement
- Table 14.3.2.5 Frequencies of Urinalysis Data
- Table 14.3.2.6 Shifts Pre-Dose versus Post-Dose of Interpretation of Hematology Data
- Table 14.3.2.7 Shifts Pre-Dose versus Post-Dose of Interpretation of Biochemistry Data

5.3.7.3 Vital signs

- Table 14.3.3.1 Summary of Vital Signs Data – Actual and Change from Pre-Dose Measurement
- Table 14.3.3.2 Vital Signs – Overall Interpretation
- Table 14.3.3.3 Shifts Pre-Dose versus Post-Dose of Interpretation of Vital Signs Data

5.3.7.4 ECG

- Table 14.3.4.1 Summary of 12-Lead ECG Data – Actual and Change from Pre-Dose Measurement
- Table 14.3.4.2 12-Lead ECG – Overall Interpretation
- Table 14.3.4.3 Shifts Pre-Dose versus Post-Dose of Interpretation of 12-Lead ECG Data

5.3.7.5 Other safety data

- Table 14.3.5 Physical Examination
- Table 14.3.6 Summary of Local Tolerability
- Table 14.3.7 Frequencies of Urine Drug Screen Data
- Table 14.3.8 Frequencies of Alcohol Breath Test Data
- Table 14.3.9 Summary of Pregnancy Tests
- Table 14.3.10 Frequencies of Anti-Drug Antibodies Test Data
- Table 14.3.11 Summary of Total Insulin and Glucose Dose Required for Insulin-Induced Hypoglycemic Clamp Procedure
- Table 14.3.12 Summary of Time to First Rescue Infusion of IV Glucose During the Hypoglycemic Clamp Procedure

